#### 6.14 Psychosocial Measures - Tailoring Variables and Predictors of Treatment Success

*Based on baseline assessment of the following measures, additional sessions will be tailored to each family's needs.*

1) *Pediatric Inventory for Parents, Parent Report* is a 42-item parent-reported measure of caregiver stress related to child chronic illness. It has shown high internal consistencies among caregivers of youth with SCD. Total scores that are  $\geq 1$  SD above the mean will be eligible for tailored sessions on caregiver stress. (5-7 mins)

2) *Adolescent Sleep Wake Scale (ASWS), Adolescent Report* is a 28-item patient-reported describing the occurrence and frequency of various behavioral sleep characteristics over the past month. It is a commonly used measure of sleep in pediatric pain with good psychometric reliability and validity. Total scores that are  $\geq 1$  SD above the mean will be eligible for tailored sessions on behavioral sleep strategies. (3-5 mins)

*3) PROMIS Pediatric Short Form - Depressive Symptoms, Self- and Parent-Proxy Report. An 8-item measure designed for youth to assess self-reported symptoms of depression, and has been utilized among a wide array of pediatric chronic illness, including chronic pain and SCD32,42. Teens reporting T-Score  $\geq 65$  will be eligible for tailored sessions focused on managing depressive symptoms. (1-2 mins)*

*4) Pain Catastrophizing Scale-Child and Parent Report is a 13-item well-validated self-report and parent-report measure of worried thoughts about pain. It is widely used in chronic pain and demonstrated strong internal consistency in SCD28,43. Total scores  $\geq 26$  by parent or child report will be eligible for tailored sessions focused on managing anxiety and fear of pain. (2-3 mins)*

*5) Pain Stages of Change Questionnaire- Adolescent and Parent Report is a 30-item measure designed to evaluate parent and adolescent perceptions of readiness to adopt a self-management approach to pain44,45. (5 mins)*

#### **6.15 Compensation**

*Parents and teens will be compensated for their time and participation for each completed study visit. Participants who do not finish the study will be paid for the visits they have completed. Parents and teens will each receive between \$435 to \$595 total, if they complete all study visits. Reimbursements are detailed below.*

*Baseline and Follow-up Surveys: Parents and teens will each receive \$25 for completing the baseline study visit, \$30 for end of treatment assessment, \$35 for 3-month assessment, and 40 for 6-month assessment.*

*Treatment and Booster Sessions: To reimburse transportation costs for attending each treatment session or to offset the costs for cellular data or WiFi usage for telehealth sessions, parents and teens will each receive \$40 for every attended session (between 7-11 sessions).*

*Qualitative Interview: Parents and teens will also each receive \$50 for completing the qualitative interview at the end of the program.*

*Blood Sample Collections: Teens will receive \$30 for completing each blood sample collection at the baseline study visit, 3-month assessment, and 6-month assessment.*

### **7.0 Data and Specimen Banking\***

*7.1 N/A*

### **8.0 Sharing of Results with Participants\***

*8.1 As a clinical service to participants, patients and parents may elect to receive aggregate data on the study findings at the completion of the study.*

## 9.0 Study Timelines\*

9.1 *Patients and parents who provide consent/assent will participate for 8 months (between 12-17 study visits). The study involves a combination of 1) assessments (4 study visits), 2) treatment sessions (6-10 study visits), 3) booster sessions (1 study visit), and 4) a qualitative interview (combined with a post-treatment assessment).*

## 10.0 Subject Population\*

10.1 *Inclusion Criteria: Youth will be eligible for inclusion if they are (a) 10-18 years old, (b) diagnosed with SCD (any genotype), (c) report chronic pain, (d) speak and read English, and (e) have not initiated new disease modifying-treatments (e.g. hydroxyurea, Endari, voxeletor, crizanlizumab, chronic transfusions) or significantly increased dosages (mg/kg) of any disease-modifying treatments in the past 3 months. As in our prior work, chronic pain classification will be based on pain frequency and persistence: 1) patient reports  $\geq 12$  pain days per month, and 2) pain frequency persisted for  $\geq 3$  months. Parents or caregivers will be eligible if they speak and read English.*

10.2 *Exclusion Criteria: Youth will be excluded if they (a) have comorbid medical conditions typically associated with pain but unrelated to SCD (e.g., rheumatologic disorders or inflammatory bowel disease); (b) are receiving chronic transfusion indicated for central nervous system risks and/or complications, previous overt strokes, or significant cognitive or developmental limitations, as per their healthcare provider or parent, that would impair completion of self-report measures or engagement in treatment sessions; and (d) received  $\geq 3$  sessions of outpatient psychological therapy for pain management in the 6 months prior to screening to ensure inclusion of patients and families who are naïve to CBT for pain. Parents or caregivers will be excluded if they have significant cognitive limitations or severe psychiatric conditions, as per the child's healthcare team or history, that would impair completion of self-report measures or engagement in treatment sessions.*

10.3 *25 child-parent dyads will be recruited from CHOA SCD clinics. Participants will include parents and children with SCD aged 10-18, which represents the developmental period when chronic pain is prevalent among youth. Patients who are 18 years old may participate without a parent or caregiver, although parent participation is preferred.*

10.4 *Community Participation (if applicable)*

- N/A

## 11.0 Vulnerable Populations\*

11.1 *The research involves children under 21 who have not attained the legal age for consent to treatments or procedures involved in research. This study involves no greater than minimal risk to children. It presents the prospect of*

*anticipated direct benefit to individual participants by teaching coping skills that may help improve pain management. Parental permission of one parent will be obtained and assent will be obtained from children to ensure voluntary participation. Parental permission, parental consent, and child assent will be documented.*

## **12.0 Local Number of Participants**

*12.1 25 parent-child dyads*

## **13.0 Recruitment Methods**

*13.1 Eligible patients will be identified for the study from new or existing SCD patients being seen through the CHOA Comprehensive Sickle Cell Program. We will use multiple recruitment strategies used in past studies. Describe the source of participants.*

*13.2 Participants in our research database who have agreed to be contacted for future studies will be contacted with a letter describing the study in a “who, what, where, and why” format and/or a personal phone call to the family to describe the study in further detail and determine interest and eligibility. Patients and parents expressing interest in the study will be provided the option to complete web-based or paper baseline measures at home, during their next scheduled outpatient clinic appointment, or during/following their inpatient admission. Verbal consent with the parent will be completed over the phone for participants from the existing study cohort. The research team will call participants to follow-up about baseline survey completion.*

*13.3 Second, all eligible patients will be approached and screened during their routine outpatient SCD appointment or inpatient admission. Parents or legal guardians of patients must provide written consent for their child to be eligible for inclusion, and youth will provide written assent. Parents will be invited to participate as well and must provide written consent for their own participation. How will eligibility be determined? Provide a detailed description of any eligibility screening done prior to enrolling subject (including whether any identifiers will be recorded – note that IP address is an identifier)*

*13.4 Third, parents and youth with SCD who meet the inclusion criteria and did not attend their scheduled outpatient appointment will be contacted by a letter describing the study. Approximately one week after the letter is mailed, a member of the research team will call the family, describe the study in further detail, and ask if they are interested in participating. Families who express an interest or agree to participate will complete verbal consent and assent over the phone and will be mailed a packet of questionnaires or a link to complete questionnaires online via a secure CHOA REDCap site, based on their preference and access to internet. The progress of the study in terms of recruitment will be monitored via a data tracking system that will allow the PI to review subject enrollment by age, gender and race.*

## **14.0 Withdrawal of Participants\***

- 14.1** Participants have the right to leave the study at any time without penalty. If participants choose to go off the study treatment or leave the study before the final planned study visit, participants may be asked to have some final study procedures completed including but not limited to follow-up surveys at the planned end of the program, and follow-up surveys at 3-months and 6-months after the program.
- 14.2** Study personnel may stop participant involvement in the study without participant consent for any reason to maintain the best interest of the participant or if participants object to any future changes that may be made in the study plan.

## **15.0 Risks to Participants\***

**15.1** Assessments: The risks for participation in the study are minimal. Study questionnaires contain potentially sensitive questions concerning pain, psychosocial functioning, and sickle cell disease, which may elicit emotional discomfort. Completion of questionnaire assessments may produce fatigue in some participants and burden related to length of assessments will be kept at a minimum.

**15.2** Treatment Sessions: The potential risk to participants is minimal. Potential risks for participants include feelings of emotional discomfort when discussing their/their child's experiences with sickle cell disease and pain management and loss of confidentiality. Some participants enjoy talking about their symptoms and functioning and learning about self-management approaches. Participants may obtain more information about their pain condition and gain confidence in their ability function despite pain. Procedures to protect against these risks are detailed in the Protections Against Risk section below. Overall, the focus group discussions do not significantly increase the participants' risk of harm beyond those risks that are inherent in ordinary daily living.

**15.3** Blood Draws: Children and adolescents have the option to consent to blood sample collection. Participation in the assessments and treatment sessions will not require consent for blood sample collection. If they consent to this opt-in portion of the study, teens will have a needle stick to get the required blood. This may cause pain, bruising, bleeding, or infection at the site of the needle stick. There should be minimal discomfort related to blood draws.

## **16.0 Potential Benefits to Participants\***

**16.1** General: To help reduce any uneasiness or discomfort about answering questions about their health, the research protocol includes standardized measures that have been widely used in other research of youth in this age range with SCD without adverse effects. Participants will be allowed to skip any

questions that they do not feel comfortable answering, will be allowed the freedom to leave during treatment sessions or the qualitative interview at any time, and will have opportunities for breaks to minimize fatigue. Participants will be informed of their right to terminate their participation in any part of data collection at any time and will be given phone numbers of the PI as well as the Emory IRB if they would like to issue a complaint or desire any additional information regarding the study. Participants will receive financial compensation for the time commitment necessary for their study participation. Participant compensation will be provided in the form of Visa cash cards. To ease the travel burden associated with transportation, participants also will be provided with gas cards.

**16.2 Blood draws:** To help minimize discomfort from blood draws, every effort will be made to coordinate study visits with clinic visits to minimize repeated blood draws and reduce the amount of time needed for additional sample collection. Well-trained phlebotomists at CHOA are experienced in conducting blood draws with minimal risk. Child life specialists are available to offer coping support to children and adolescents, if needed.

**16.3 Depression Screening:** In the event that one of the procedures reveals indicators of significant depressive symptoms or suicidal ideation, a standard suicide-risk plan will be implemented. [name] and her research staff are already trained in a standard risk assessment protocol that has been successfully implemented in [name] prior studies. Research staff will already be reviewing baseline assessment measure to determine the need for tailored sessions. The treatment program will be delivered by highly trained psychology postdoctoral fellows supervised by the PI. In the event that a participant endorses clinically significant depressive symptoms, suicidal ideation, or reveals a history of abuse on questionnaires or during treatment sessions, a risk assessment will be conducted by the psychology fellows under [name] supervision. [name] is a licensed clinical psychologist and will be available 24 hours a day to be called via cell phone to address crisis questions. Psychiatric or other life crises that are high risk and imminent will be acted upon immediately with staff linking participants to appropriate crisis services (e.g., a referral to the ED (if necessary), community agencies for ongoing care). These are reviewed immediately with the clinically responsible PI and/or primary co-mentor ([name]), who is also a licensed clinical psychologist. Lower risk and less imminent crises will result in an attempt to help the participant devise a plan for treatment and/or safety. For example, major stresses, availability of social supports, access to treatment, and plans for safety will be discussed in detail with the participant, and appropriate referrals for treatment will be provided. These cases will be reviewed within 24 hours by the clinically responsible PI and mentors. All actions taken will be documented on a case report form. Based on our prior experience in similar psychosocial pain research in SCD, we anticipate this risk to be very low.

**16.4** Benefits to participant or future benefits. Participation in the clinical trial may or may not directly benefit participants. This study is designed to learn more about how teens with chronic sickle cell pain respond to the program and if it helps them manage their chronic pain. Although we do not know for certain whether the treatment will reduce pain, the study results will allow us to develop better treatment programs which might be used to help others in the future. This will provide critical knowledge for the further intervention refinement and testing in a controlled trial in a future study. The potential risks of participation to participants are considered to be minimal in relation to the potential gain.

## **17.0 Data Analysis, Management\* and Confidentiality**

**17.1** Data Management. All data will be entered into REDCap (supported by both Emory and CHOA), a secure web-based application for managing surveys and databases online, and exported into SPSS. The first step will be to compute descriptive statistics for all measures (means, standard deviations, range and skewness). This process will allow us to determine if there are any extreme outliers and whether the variables are normally distributed. If a variable is not normally distributed, log transformations will be used in all further analyses. Bivariate correlations among demographic variables and variables of interest will be examined to identify any meaningful covariates that will need to be controlled in further analyses. Missing data will be handled by using Multiple Imputation or Maximum Likelihood methods of handling missing data.

**17.2** Treatment Feasibility. Feasibility will be assessed using 4 metrics:

- 1) Study recruitment and enrollment statistics, such as proportion of eligible participants approached for the study who consent to participate
- 2) Treatment adherence as demonstrated by drop out rate, session completion, missed/rescheduled treatment sessions, therapist ratings of participants' homework completion, including the proportion of participants who attend at least 80% of sessions
- 3) Proportion of participants who complete study assessments
- 4) Participant ratings on whether they thought the Back2Life program is a reasonable approach for chronic pain management, if the program was helpful, could be integrated into their lifestyle, and description of barriers in implementing the program.

**17.3** Treatment Acceptability. Acceptability of the intervention will be assessed through the Treatment Evaluation Inventory Short Form as well as qualitative interviews that will elicit perceptions about treatment content (utility, appropriateness) and format (convenience, number and length of sessions). See Appendix B for Interview Guide. Audio recordings of qualitative interviews will be transcribed for analysis. A coding system for thematic domains

and a coding scheme will be developed. Qualitative data will be analyzed using MAXQDA. Interview data will be coded by two independent reviewers to enhance confirmability and dependability of conceptual domains. Describe the steps that will be taken to secure the data (e.g., training, authorization of access, password protection, encryption, physical controls, certificates of confidentiality, and separation of identifiers and data) during storage, use, and transmission.

**17.4** Preliminary efficacy will be examined by calculating standard effect sizes and 95% confidence intervals on primary outcomes (pain interference, pain, coping) at post-treatment and 3- and 6-month follow-up. Changes in primary outcomes over time will be assessed using repeated measures ANOVA. Comparisons between time points will be made using paired tests or Wilcoxon tests. In an adjusted analysis, potential control covariates (e.g., child age, number of sessions, changes in treatment) will be examined as appropriate. Based on past CBT pain trials, pain reductions typically occur from baseline to follow-up and independent of changes in pain interference. To account for potential non-significant changes in pain intensity, we will examine individual clinically significant ( $\geq 30\%$ ) reductions in pain and interference.

**17.5** Power Analysis: We are not attempting to fully power this proof-of-concept study and will only examine preliminary efficacy using exploratory analyses. Preliminary power analyses were based on meta-analysis of CBT for pediatric chronic pain. We estimate an effect size of  $d=.55$  for pain reduction at follow-up (30% pain reduction). A sample size of  $n=25$  would achieve power estimates of approximately 80%.

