#### **6.12 Primary Treatment Outcomes**

- 1) PROMIS Pediatric Short Form-Pain Interference, Self- and Parent-Proxy Report is an 8-item self-report measure that will assess functional interference due to pain in the past 7 days. PROMIS Pediatric measures have been well validated among youth with SCD and chronic pain in inpatient and outpatient settings31-34. (2-3 mins)*
- 2) Sickle Cell Pain Burden Interview for Youth, Self-Proxy Report is a brief, validated measure of pain burden in 7-21 year olds. It demonstrated strong reliability and validity among youth with SCD from inpatient and outpatient settings35. Patient self-report and parent-proxy report of total pain days in the past month and duration of chronic pain will also quantify pain frequency1,35. (2-3 min)*
- 3) PROMIS Pediatric Short Form-Pain Behaviors, Parent-Proxy Report is an 8-item measure completed by parents that assesses pain behaviors displayed by their child in the past 7 days. PROMIS Pediatric measures have been well validated among youth with SCD in inpatient and outpatient settings (2-3 min)*

4) *Child Self-Efficacy Scale, Self- and Parent-Proxy Report* is a well-established, 7-item measure of self-efficacy for functioning despite pain for 8-19 year olds. It demonstrated good internal consistency and validity among youth with a variety of pain problems. (2-3 min)

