#### 6.13 Secondary Treatment Outcomes

1) *Healthcare utilization will be extracted from the medical record to document the total number of emergency department (ED) visits and admissions for pain for 6-months and 12-months pre- and post-treatment.*

2) *Opioid use will be calculated based on participant completion of daily diaries for 1-week at each assessment visit. Participants will record opioid use daily (presence/absence). Opioid use also will be documented on daily diaries throughout the course of treatment.*

3) *Inflammatory biomarkers, including but not limited to, proinflammatory cytokines and markers, such as interleukin -18 (IL-18), interleukin – 6 (IL-6), interleukin – 8 (IL-8), tumor necrosis factor – alpha (TNF- $\alpha$ ), c-reactive protein (CRP), brain-derived neurotrophic factor (BDNP), and interferon gamma (INF- $\gamma$ ) will be analyzed. Plasma concentrations for each biomarker will be determined by a custom multiplex kit (e.g., FirePlex-384 Multiplex Assay by abcam), an immunoassay panel detected by flow cytometry used for simultaneous quantitative measurement in a single sample with high sensitivity and high throughput capacity. All samples will be analyzed in triplicate.*

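### Section 17.1's log rule takes in outcomes that can be zero, and the usual repeated-measures ANOVA in 17.4 does not carry out 17.1's maximum likelihood option

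*Combined protocol and SAP*

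**What the plan says.** Section 17.1 begins with a check of every measure: "compute descriptive statistics for all measures (means, standard deviations, range and skewness". Its rule for what follows is "If a variable is not normally distributed, log transformations will be used in all further analyses". It gives no cut-off for non-normality, no treatment of zeros and no exception. On missing data it says: "Missing data will be handled by using Multiple Imputation or Maximum Likelihood methods of handling missing data". It does not choose between the two.

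Several outcomes have a floor of zero:
- Section 6.13 counts the "total number of emergency department (ED) visits and admissions for pain for 6-months and 12-months pre- and post-treatment".
- For opioids, section 6.13 says: "Participants will record opioid use daily (presence/absence". The score is not defined; summing the one-week diary gives 0 to 7 days.
- Section 6.12 lists, among the primary outcomes, "Patient self-report and parent-proxy report of total pain days in the past month".

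In section 10.1, "chronic pain classification will be based on pain frequency and persistence", with at least 12 pain days a month by the patient's own report.

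Section 17.4 names repeated-measures ANOVA for change over time in the primary outcomes, and a paired or Wilcoxon test between time points, with no rule for choosing between those two. It also plans standardised effect sizes and an individual analysis of reductions of 30% or more. It names no model for the secondary outcomes, and no mixed or count model appears anywhere.

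**The concern.** The log of zero does not exist. Followed literally, the rule removes every pair with a zero on either side. An analyst who avoids this by adding a constant must pick one, and the plan gives none. Choosing it after seeing the data is what a written rule should prevent.

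For pain days the shape makes this worse. A patient who reported at least 12 days at entry can report zero only later, after a very good response. Such values form a left tail. A log lengthens a left tail, so it can worsen the non-normality it is meant to cure.

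The second point is a mismatch between 17.1 and 17.4. Repeated-measures ANOVA as usually run drops anyone with a missing visit. If maximum likelihood is the option taken from 17.1, that ANOVA does not deliver it. It would also discard people who leave treatment but return only some of the surveys that section 14.1 may ask of them.

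Section 5.0 uses this trial to judge whether the treatment merits a randomised trial, so the size of the reported effects has some bearing.

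**Working it through.** **The plan's own figure.** Section 17.5 gives about 80% power for n=25 and d=0.55. Taking d as mean change over SD of change, two-sided 5% (assumed): Φ(0.55×√25 − 1.96) = Φ(0.79) = 78.5%. The noncentral t gives 75.1%. The figure reproduces approximately and is not in dispute.

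Everything below rests on assumed rates, because the documents give no visit rates, spreads or missing-visit rates.

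**Counts, true fall 33%.** Pairs kept by a plain log, Poisson:
- means 1.5 then 1.0: (1−e^−1.5)(1−e^−1.0) = 0.777×0.632 = 0.49
- means 3 then 2: (1−e^−3)(1−e^−2) = 0.950×0.865 = 0.82

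With overdispersion shared within a participant (gamma shape 1.5, simulated) these become 0.41 and 0.64.

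Reading of the fall = 1 − exp(mean log after − mean log before). For Poisson 1.5 then 1.0 with constant 1: mean log(x+1) goes from 0.792 to 0.573, so 1 − e^−0.218 = 20%. Likewise:

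| Scenario | Plain log | +1 | +0.5 | +0.1 |
|---|---|---|---|---|
| Poisson 1.5/1.0 | 16% | 20% | 26% | 41% |
| Overdispersed 1.5/1.0 | 21% | 17% | 22% | 34% |
| Poisson 3/2 | 27% | 26% | 32% | 42% |
| Overdispersed 3/2 | 27% | 23% | 27% | 38% |

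The reason is visible in one step: a change from 1 to 0 is ln(c/(1+c)), which is −0.69, −1.10 or −2.40 for c = 1, 0.5 or 0.1.

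Simulated power at n=25:

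| Means | Plain log | log(x+1) | Wilcoxon, raw |
|---|---|---|---|
| 1.5/1.0 | 14-16% | 28-32% | 30-32% |
| 3/2 | 37-38% | 48-53% | 54-56% |

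So a constant of 1 costs 0-6 points against Wilcoxon; the large loss belongs to the plain log.

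**Opioid days of 7** (40% to 27%, or 60% to 40%, of days): a plain log keeps 60-97% of pairs. A true fall of 32-33% reads 26-32% with constant 1 and 39-51% with 0.1.

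**Pain days.** Baseline N(20, 5) limited to 12-30; follow-up a fraction of baseline plus noise; n=25; standardised paired effect:

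| Follow-up pattern | Raw | log(x+1) | Loss |
|---|---|---|---|
| 2-4 of 25 set to exactly zero | 1.04 | 0.67 | 36% |
| 2 or 4 strong responders spread over 0-6 days | 1.11 | 0.83 | 25% |
| Wider noise (SD 7), about one natural zero | 0.90 | 0.76 | 16% |
| Almost no zeros | 1.20 | 1.04 | 13% |

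In the first row, mean skewness goes from about −0.5 raw to −1.8 after the log. The rule fires in anything from about 0% to 56% of samples. With |skewness|>1 (an assumed cut-off) it is at most 12%; the high values need Shapiro-Wilk and implanted zeros.

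**Missing visits.** With a share q missing independently at each of three follow-ups, complete cases number 25(1−q)³: 21.4, 18.2 and 15.4 for q = 5%, 10% and 15%.

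Omnibus power: SD 1, correlation 0.5, means 0, .55, .55, .55. The sum of squares about the mean is 0.4125² + 3×0.1375² = 0.2269, so λ = n×0.2269/0.5 = 0.4538n, with 3 and 3(n−1) degrees of freedom:

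| q | n kept | λ | ANOVA, formula | ANOVA, simulated | Mixed model, simulated |
|---|---|---|---|---|---|
| 0 | 25 | 11.3 | 79% | 78-81% | same data |
| 5% | 21 | 9.5 | 71% | 70-73% | 78-79% |
| 10% | 18 | 8.2 | 63% | 62-64% | 76-78% |
| 15% | 15 | 6.8 | 53% | 53-55% | 76% |

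The standard error of the 6-month change from available pairs against maximum likelihood is .205/.204, .212/.211 and .214/.218. Pairwise comparisons are barely touched.

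**The case against.** **Section 17.4 already allows Wilcoxon.** True, and that is much of the remedy. But 17.1 applies the log to all later analyses and the two sections are not reconciled. A signed-rank test on logged differences has the same gap at zero.

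**No document says the healthcare counts will be reported as back-transformed percentages.** Correct: section 2.4 only says reductions will be explored. A mean log change is also not meant to equal a ratio of arithmetic means. So the count table does not show an error in a planned result. It does show that the same data give different sizes of change according to an unstated constant.

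**Power is hardly affected.** With a constant of 1, this stands. A reader might infer that the rule halves power; that follows only if undefined values are simply dropped.

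**The pain-day loss is built into the assumptions.** Largely right. A reader might infer that the effect shrinks by a third or more. That needs several participants at exactly zero while the others average about 15 days, which nothing in the documents supports. With a plain log the standardised effect does not shrink (1.04-1.07), though it is then computed without the best responders. Nor are zeros confined to follow-up throughout: the 12-day floor is by patient report, and parent-proxy pain days have no such floor.

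**ANOVA and maximum likelihood can coexist.** A reader might infer that the plan cannot be run. The documents do not support that. Multiple imputation can feed the ANOVA, and a compound-symmetry model fitted by REML is its likelihood form. The conflict is between the usual complete-case procedure and one of two permitted options.

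**Conclusion.** Both points hold in limited form.

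The log rule is unsuited to outcomes that can be zero. The effect is clearest for the exploratory healthcare counts: 41-82% of pairs kept under a plain log, or a true 33% fall read as 17-42% across constants from 1 to 0.1. For pain days it is conditional on the variable being judged non-normal, and then costs roughly 15-35% of the standardised effect, depending on how many participants end near zero. The individual 30% analysis needs no log.

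The ANOVA in its usual form leaves 17.1's maximum likelihood option unused. Under the assumed losses, omnibus power falls to about 70-73%, 62-64% or 53-55%, against about 76-79% for a mixed model. This concerns the primary outcomes only, since 17.4 names the ANOVA for those alone.

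All rates are assumptions. Severity is low to moderate: section 17.5 calls efficacy exploratory and not fully powered, and the direction of effect does not change.

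**What to change.** - In 17.1, limit the log rule to strictly positive, right-skewed variables, such as the biomarkers in section 6.13 ("Plasma concentrations for each biomarker will be determined by a custom multiplex kit"), with a stated rule for values below detection.
- Analyse visit and admission counts, pain days and opioid days untransformed, with the Wilcoxon test already in 17.4, or a count or binomial model where it fits. Define the opioid score.
- State that the individual 30% analysis uses raw values.
- In 17.4, replace repeated-measures ANOVA with a linear mixed model (REML, visit as a category, all observed visits). This carries out the maximum likelihood option.

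Whether efficacy is judged in completers, as section 2.3 words it, or in all who start treatment is a separate question, and this fix leaves it alone.

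The cost is SAP wording only; no new data or visits are needed and the software is standard. The drawback is that count models may not fit at n=25, so the rank test should be named as the fallback.
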